6.2. Hemophilia A history factor analysis

- 1) Descriptive statistics (n, mean, median, SD, minimum and maximum)
 - ① Duration of the disease (Year)

Statistical Analysis Plan for rPMS

- 2) Frequency statistics (frequency and percentage)
 - ① Genetic mutation of factor VIII (Yes, No, Unknown)
 - ② Previous exposure to plasma-derived factor VIII (Yes, No, Unknown)
 - ③ Previous used factor VIII therapy (Yes, No)
 - ④ Personal history of allergic reactions to factor VIII products (Yes, No)
 - ⑤ Family history of hemophilia A [Yes (Parents, Brothers, Other), No]
 - ⑥ Family history of factor VIII inhibitors (Yes, No)
 - ⑦ Family history of allergic reactions to factor VIII products (Yes, No)
 - ⑧ Severity (Mild, Moderate, Severe, Unknown)

6.3. Medical History

- 1) Frequency and percentage for renal/hepatic status (Yes, No) will be presented.
- 2) Past/present disease
 - ① Past disease, present disease depending on time will be analyzed, respectively.
 - ② Frequency and percentage for past/present disease status will be presented and past/present disease classified by 092 version of WHO-ART in detail will be presented in each frequency and percentage.

6.4. Concomitant Treatments/Therapy

- 1) Concomitant medication status (Yes, No) will be presented in frequency and percentage and concomitant medication classified by 092 version of WHO-ART in detail will be presented in n, percentage and frequency.
- 2) Concomitant therapy status (Yes, No) will be presented in frequency and percentage and concomitant therapy classified by 092 version of WHO-ART in detail will be presented in n, percentage and frequency.

6.5. Administrative Status for Medicinal product

- 1) Duration of administration, single infusion dosage and total infusion dosage of Xyntha solofuse prefilled syringe administered for the purpose of on-demand treatment will be presented by n, mean, SD, median, minimum and maximum.
- 2) Duration of administration, single infusion dosage and total infusion dosage of Xyntha solofuse prefilled syringe administered for the purpose of prophylactic therapy will be presented by n, mean, SD, median, minimum and maximum and total frequency of infusion will be presented frequency and percentage.

Statistical Analysis Plan for rPMS

6.6. Safety Analyses

Safety analysis will be performed based on data of safety analysis set. All adverse events in CRF will be classified by System Organ Class (SOC) and Preferred Term (PT) according to the Korean 092 Version of WHO-ART distributed by Korean Ministry of Health and Welfare.

- 1) All adverse events occurred during or after administration of this medicinal product will be summarized by frequency and percentage (n, percentage) by categorizing as follows. Also, it will be presented in n, incidence proportion, 95% confidence interval of incidence proportion and number of events for each SOC and PT.
 - ① Frequency analysis of adverse event/adverse drug reaction
 - ② Frequency analysis of serious adverse event/serious adverse drug reaction
 - ③ Frequency analysis of unexpected adverse event/unexpected adverse drug reaction
- 2) All adverse events by categorizing as follows will be presented in number of events and percentage.
 - ① Occurrence status of adverse event and adverse drug reaction by its severity
 - Mild
 - Moderate
 - Severe
 - ② Occurrence status of adverse event and adverse drug reaction by its action taken related with administrating this medicinal product.
 - No change
 - Dosage reduced
 - Dosage increased
 - Temporarily discontinued
 - Permanently discontinued
 - Not applicable
 - ③ Occurrence status of adverse event and adverse drug reaction by other action taken
 - Therapeutic prescription
 - Other
 - No treatment
 - ④ Occurrence status of adverse event and adverse drug reaction by its seriousness
 - If a death is caused;
 - If it is life-threatening (risk of an immediate death);
 - If hospitalization or extended duration of hospitalization is required;
 - If persistent or significant disability or malfunction is induced (substantial disruption in the ability to conduct normal life functions);
 - If congenital anomalies/birth defects are induced.

Statistical Analysis Plan for rPMS

- Important medical event: if it is determined that the event may jeopardize the patient or may require intervention to prevent one of the other outcomes listed in the definition above
- ⑤ Incidence of adverse event and adverse drug reaction by outcome
- Yes
 - Unknown
 - No (disappeared)
- ⑥ Occurrence status of adverse event and adverse drug reaction by its causality assessment.
- Related to this medicinal product:
 - I. Certain
 - II. Probable/likely
 - III. Possible
 - V. Conditional/unclassified
 - VI. Unassessable/unclassifiable
 - Not related to this medicinal product:
 - IV. Unlikely
- 3) Occurrence status of adverse event by demographics and baseline characteristics
- Occurrence status of adverse events will be presented in frequency and percentage and incidence proportion with 95% confidence interval based on categorical variables of demography and baseline characteristics of the patients (sex, age group, past/present disease status, renal/hepatic disorder status). To identify statistically significant difference in occurrence of adverse events among demography and baseline characteristics, Chi-square test or Fisher's exact test will be performed.
- 4) Occurrence status of adverse event by concomitant treatment/therapy
- Occurrence of adverse events will be presented in frequency and percentage and incidence proportion of adverse events with 95% confidence interval by concomitant treatment status and concomitant therapy status. To identify statistically significant difference in occurrence of adverse events among concomitant treatment status, concomitant therapy status, Chi-square test or Fisher's exact test will be performed.
- 5) Analysis of factors that affect safety
- Logistic regression analysis will be performed and an odds ratio with 95% confidence interval will be presented to identify the factors that affect occurrence of adverse events in demography and baseline characteristics (sex, age group, past/present disease status, renal/hepatic disorder status), or concomitant treatment status, concomitant therapy status, etc.

Statistical Analysis Plan for rPMS

- 6) Test of difference for laboratory data before and after administration.
Laboratory data before and after administration will be presented by descriptive statistics and test of difference for laboratory data before and after administration will be performed by using paired t-test (or Wilcoxon signed-rank test). This analysis will be performed if possible.
- 7) Distribution for special patient populations (children (age<19), elderly (age≥65), renal disorder, hepatic disorder, pregnant woman) will be presented. Also, adverse events and adverse drug reactions collected by these groups will be presented in incidence proportion and number events of it for each SOC and PT.
- 8) Distribution for subgroups status (patients with prior treatment experience/patients with prior non-treatment experience) will be presented. Also, adverse events and adverse drug reactions collected by these groups will be presented in incidence proportion and number events of it for each SOC and PT.
- 9) Distribution for excluded safety patient groups will be presented. Also, adverse events and adverse drug reactions collected for these groups will be presented in incidence proportion and number events of it for each SOC and PT.

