7.3. Variables

7.3.1. Safety Variables

This study will investigate clinical nature, incidence rates, duration, severity, discontinuation due to adverse events, results and possible causality of adverse events.

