7.7. Data Analysis

7.7.1. Evaluation parameters

1) Case parameters

- Descriptive analysis will be performed regarding the total number of collected CRFs, the number of safety evaluation subjects, the number of efficacy evaluation subjects, the number of discontinued cases and their reasons.

2) Safety parameters

- Safety parameters will be evaluated.
- The incidence of adverse events sorted by body organ and disease/symptom
- If the data is adequate, sub-analysis can be performed for each factor that is considered to affect safety.
- Clinically significant abnormalities found in laboratory tests (if conducted)

3) Efficacy variables

- On-demand treatment
 - Responses to all the injection of the Xyntha Solofuse prefilled syringe used to treat bleeding (4 point scale: excellent, good, moderate, and no response)
 - Number of observations of less than expected therapeutic effect (LETE) (LETE: “no response” rated after each infusion of 2 consecutive infusions within 24 hours after on-demand treatment)
 - In case of bleeding: The number of infusions of Xyntha Solofuse prefilled syringes used to treat each new bleeding episode is rated.
 - Mean infusion dosage
- Prophylactic Therapy
 - Percentage of the study subjects who have experienced bleeding (overall, spontaneous)
 - Annualized bleeding rates (ABRs)
 - Number of observations of less than expected therapeutic effect (LETE)

(LETE: Atypical bleeding occurring within 48 hours after administration of the Xyntha Solofuse Prefilled Syringe by dosage for the prevention of bleeding (spontaneous/at traumatic))

- Mean infusion dosage
- Total factor consumption
- If the data are adequate, sub-analysis can be performed for each factor that is considered to affect the efficacy.

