4.6. Safety Endpoints

- 1) The incidence and number with 95% confidence Interval for all adverse events/adverse drug reactions investigated within 6 months from initial administration after at least 1 dose of Xyntha solofuse prefilled syringe (If the study subject has not completed the 6-month treatment, relevant data should be collected based on the medical records within the 30 days after the last administration of the drug)

- ① Severity
- ② Action taken
- ③ Seriousness
- ④ Outcome
- ⑤ Causality assessment

2) Laboratory Test

- ① Blood test(Hemoglobin, Hematocrit, RBC, WBC, Platelet Count, ESR, CRP)
- ② Biochemical test(AST(SGOT), ALT(SGPT), ALP, BUN, Creatinine, Factor VIII Inhibition Factor Hemoglobin)
- ③ Urine examination(Protein/Albumin, Glucose/Sugar, Hemoglobin/Blood)

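### SAP 6.6(2) reports AE severity and action taken only as event counts with an undefined percentage, so no subject-level rate of severe AEs or of AEs leading to permanent discontinuation is planned

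*SAP*

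**What the plan says.** SAP 4.6(1) defines the AE endpoint as "The incidence and number with 95% confidence Interval for all adverse events/adverse drug reactions investigated within 6 months from initial administration". Five items are listed beneath it: severity, action taken, seriousness, outcome and causality assessment.

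SAP 6.6 then splits the analysis in two.

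- **6.6(1)** covers AEs/ADRs, serious AEs/ADRs and unexpected AEs/ADRs. Besides frequency and percentage it requires "n, incidence proportion, 95% confidence interval of incidence proportion and number of events for each SOC and PT".
- **6.6(2)** covers severity, action taken with the drug, other action taken, seriousness criteria, outcome and causality grade. Its instruction is: "All adverse events by categorizing as follows will be presented in number of events and percentage". One of the action-taken categories is "Permanently discontinued".

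On the protocol side, section 7.3.1 states: "This study will investigate clinical nature, incidence rates, duration, severity, discontinuation due to adverse events, results and possible causality of adverse events". Section 7.7.1 plans a descriptive account that includes "the number of discontinued cases and their reasons". No analysis in the SAP takes this up. The subject accounting in SAP 3.4 concerns exclusions from the safety analysis set, not patients who stopped treatment.

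**The concern.** A count of events and a count of patients answer different questions. The usual safety questions are what fraction of treated patients had a severe AE, and what fraction had an AE that led to permanent discontinuation. An event count cannot answer either, because one patient with repeated events contributes several times.

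At stake is part of the secondary objective, which is overall safety. The study could report in full under its SAP and still not state, with its uncertainty, how many patients had a severe AE or an AE leading to permanent discontinuation. A reader who took the 6.6(2) percentage for a patient risk could be misled, and the SAP gives no denominator to prevent that.

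**Working it through.** The plan states no figure for this point, so there is nothing to reproduce. The check is a comparison of the texts, followed by an illustration with assumed counts.

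**Step 1: does the SAP distinguish subjects from events?** Yes. In 6.6(1) the list "n, incidence proportion, 95% confidence interval of incidence proportion and number of events for each SOC and PT" names n and number of events as separate quantities. The number of events in 6.6(2) is therefore not naturally read as shorthand for a number of subjects.

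**Step 2: which results have a subject-level rate?**

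| Result | Subject-level incidence with CI | Event count and percentage |
|---|---|---|
| Any AE/ADR | 6.6(1) | 6.6(1), events |
| Serious AE/ADR | 6.6(1) | 6.6(1); by criterion in 6.6(2) |
| Unexpected AE/ADR | 6.6(1) | 6.6(1), events |
| Related vs not related | 6.6(1), as ADR | 6.6(2), by grade |
| Severity (mild, moderate, severe) | none | 6.6(2) |
| Action taken, incl. permanent discontinuation | none | 6.6(2) |

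**Step 3: does another item fill the last two rows?** No. Items 6.6(3) to (5) relate overall AE occurrence to baseline characteristics and concomitant treatment. Item (6) concerns laboratory values. Items (7) to (9) present AEs and ADRs by SOC and PT in special populations, by prior treatment and in excluded subjects. None is broken down by severity or action taken. Serious AEs do not stand in for severe AEs, since the SAP lists severity and seriousness separately in both 4.6 and 6.6(2).

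**Step 4: what information is lost?** Inputs for the illustration:

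- N = 86 subjects, the minimum number for whom Protocol section 5 expects data.
- 6 severe events. This is assumed; the documents give no expected AE count.
- Exact (Clopper-Pearson) 95% intervals. This is also assumed, because the SAP names no CI method.

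Subject-level incidence = subjects with at least one severe event / N.

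- All six events in one subject: 1/86 = 1.2% (95% CI 0.03% to 6.3%).
- One event in each of six subjects: 6/86 = 7.0% (95% CI 2.6% to 14.6%).

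Under 6.6(2) both cases print as six events with the same percentage. If that percentage is taken over all events, its value also depends on the total: 6/20 = 30%, 6/40 = 15%, 6/80 = 7.5%, with all three totals assumed. It stays the same whether one patient or six are affected.

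**The case against.** The strongest reply is that SAP 4.6(1) defines a single quantity, the incidence of AEs/ADRs with a CI, and that 6.6(1) delivers it. The five items beneath carry no wording such as by or for each, and can be read as attributes to describe, which 6.6(2) does. That reading is tenable. A reader might infer that 6.6(2) flatly contradicts 4.6 for all five attributes, and the documents do not support so much. The gap survives on either reading, because neither yields a patient-level rate for severe AEs or for AEs leading to permanent discontinuation.

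Further points on the other side, and what stands of each:

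- **Causality and seriousness.** Item 6.6(1) includes "Frequency analysis of adverse event/adverse drug reaction" and the same for serious events, so ADR incidence and overall serious AE incidence are already at subject level with a CI. This stands, and neither is part of the point. Only the individual causality grades and seriousness criteria are event-based.
- **Discontinuation.** Protocol 7.7.1 plans a count of discontinued cases with reasons, which could identify patients who stopped because of an AE. This stands in part: it is a patient-level count, but without a planned rate or interval, and the SAP does not carry it forward. It says nothing about severity.
- **Protocol requirement.** Section 7.3.1 names things to investigate and does not demand a subject-level incidence for each. Section 7.7.2.1 asks for number and incidence by body organ and disease or symptom, which 6.6(1) supplies. So this is not a breach of the protocol.
- **Outcome.** The outcome item in 6.6(2) is headed as an incidence, but the lead sentence still prescribes events and a percentage. This is a small inconsistency within that item and does not reach severity or action taken.
- **Size.** It is tempting to say that the table overstates patient risk by a given multiple. That would need an assumed total of events, an assumed clustering within patients, and the further assumption that the unstated denominator is all events. The documents support none of these.

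**Conclusion.** The point holds for two results: severe AEs, and AEs leading to permanent discontinuation. For both, the SAP plans an event count and a percentage of undefined base, with no number of patients, incidence proportion or interval. No other SAP item supplies them.

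The conclusion rests on the text alone. The contrast of 1.2% and 7.0% of 86 subjects is an assumed illustration of the ambiguity, not an estimate of any bias.

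The consequence is moderate. The primary objective, detection of factor VIII inhibitor, is unaffected, and no hypothesis or decision rule uses these tables. The correction should still be made: the affected results belong to the overall safety objective, and the SAP already uses the needed format in 6.6(1).

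**What to change.** In SAP 6.6(2), at least for severity and for the action-taken category "Permanently discontinued":

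1. Beside the event count, add the number of subjects with at least one such event, the incidence proportion over the safety analysis set, and its 95% CI, as in 6.6(1).
2. Count each subject once, at worst severity, in the severity table.
3. State the denominator of the event percentage, for example all AEs or all ADRs reported in the safety analysis set.

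It would also help to say in SAP 4.6(1) whether the five listed items are separate incidence endpoints or descriptive attributes, and to carry the Protocol 7.7.1 count of discontinued cases and reasons into the SAP so that it can be reconciled with the new row.

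The cost is SAP wording and a few extra columns in tables already planned. No new data are needed, since the case report form records AEs by subject.

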5. RATIONALE AND BACKGROUND

Xyntha Solofuse prefilled syringe was approved on March 31, 2014 in Korea. The Xyntha Solofuse prefilled syringe is administered by intravenous infusion after reconstitution of the freeze-dried powder with the diluent (0.9% Sodium Chloride). This drug consists of the identical ingredients with the previous Xyntha injection, and the drug and the diluent are supplied within the prefilled dual-chamber syringe. As required for all new drugs approved by the Ministry of Food and Drug Safety (MFDS), information on the safety and efficacy of the new drug should be provided based on the study conducted with at least 600 study subjects who are administered this drug in the setting of routine practice for 4 years from the approval date (March 31, 2014 - March 30, 2018). This non-interventional post-marketing surveillance (PMS) study is an obligation to the MFDS. However, it is expected that about 95 subjects who received this drug should be recruited and registered as study subjects. Considering the number of subjects who meet the analysis exclusion criteria, safety and efficacy information for at least 86 subjects will be collected for all subjects who received this drug during the study period. Background information on Xyntha Solofuse prefilled syringe can be obtained from the current version of the local product document, which is the single reference safety document (SRSD) for information relating to the Xyntha Solofuse prefilled syringe in this study.

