7.2.5.2. Concomitant Therapy

With regard to all the concomitant therapies, the name, dosage, route of administration, period and treatment purpose should be recorded in the case report form of each study subject.

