7.5. Study Size

The calculation of sample size is not applicable for this study. At least 600 study subjects will be enrolled in this study to meet the MFDS requirements. In this study, 14 sites conduct complete enumeration study data collection for more than 86 subjects who administered this drug during study period .

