4.4. Concomitant Treatments/Therapy

- 1) Concomitant medication (Status (Yes/No), Level1, Level2 of concomitant medication classified by latest version of KIMS code)
- 2) Concomitant therapy (Status (Yes/No), Level1, Level2 of concomitant therapy classified by latest version of KIMS code)

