5.1. Analysis Principles

Statistical analysis will be conducted after database is locked and performed using SAS software version 9.4 according to this statistical analysis plan. If statistical analysis methods are changed, it will be described in the final study report.

Continuous variables will be summarized by the descriptive statistics (n, mean, median, SD (standard deviation), minimum, and maximum). Categorical variables will be presented in the frequency distribution table (n, %).

In case of statistical hypothesis testing, two-sided test will be conducted under 5% significance level and the p-value of each test result will be presented in the summary table.

6. Statistical Analyses

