4) Overall efficacy assessment will be classified as effective/not-effective as follows, presented in frequency and percentage of it.

- ① On-demand treatment

- [Effective]: Subjects with whom the best responses 'Excellent' or 'Good' or 'Moderate'.
- [Not-effective]: Subjects with whom the best responses 'No response'.

- ② Prophylactic Therapy

- [Effective]: Subjects who haven't experienced any atypical bleeding within 48 hours after administration of the Xyntha Solofuse Prefilled Syringe.
- [Not-effective]: Subjects who have experienced at least once atypical bleeding within 48 hours after administration of the Xyntha Solofuse Prefilled Syringe.

5) Efficacy assessment by demographics and baseline characteristics

Classified overall assessment (effective/not-effective) will be presented in frequency and percentage based on categorical variables of demography and baseline characteristics (sex, age group, past/present disease status, renal/hepatic disorder status). To identify statistically significant difference of frequency distribution of classified overall assessment (effective/not-effective) among demography and baseline characteristics, Chi-square test or Fisher's exact

Statistical Analysis Plan for rPMS

test will be performed.

- 6) Efficacy assessment by concomitant treatment (Concomitant Treatments/Therapy status)
Classified overall assessment (effective/not-effective) will be presented in frequency and percentage for concomitant treatment status (Concomitant Treatments/Therapy status). To identify statistically significant difference of frequency distribution of classified overall assessment (effective/not-effective) among concomitant treatment status, concomitant therapy status, Chi-square test or Fisher's exact test will be performed.
- 7) Analysis of factors that affect efficacy
Logistic regression analysis of multivariate analysis will be performed and presented an odds ratio with 95% confidence interval to identify the factors that affect classified overall assessment (effective/not-effective) in demography and baseline characteristics of the patients (sex, age group, past/present disease status, renal/hepatic disorder status), or concomitant treatment status, concomitant therapy status, etc.

7. Reporting Principles

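### Concomitant-treatment status in the SAP is undated and does not exclude drugs started to treat an adverse event, so its tested and modelled association with adverse events can be biased upward

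*SAP*

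**What the plan says.** **Collection.** Protocol 7.2.5.1 collects drugs and therapies given concomitantly with the product, over an observation period of up to 6 months (Protocol 7.1), with no limit on start date. For all concomitant therapies, Protocol 7.2.5.2 says that "the name, dosage, route of administration, period and treatment purpose should be recorded in the case report form".

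**Definition for analysis.** SAP 4.4 reduces this to "Concomitant medication (Status (Yes/No") plus coding levels, and treats therapy in the same way. SAP 6.4 tabulates the Yes/No status. Neither section gives a reference date, an ordering relative to the event or an exclusion by purpose.

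**Use for safety.** SAP 6.6(4) presents the "incidence proportion of adverse events with 95% confidence interval by concomitant treatment status and concomitant therapy status" and adds a Chi-square or Fisher's exact test to identify significant differences. SAP 6.6(5) lists the status among the factors for a logistic regression with odds ratios and 95% intervals. SAP 5.1 says that a "two-sided test will be conducted under 5% significance level" and that p-values go in the summary tables.

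**Use for efficacy.** SAP 6.7(6) says: "Classified overall assessment (effective/not-effective) will be presented in frequency and percentage for concomitant treatment status (Concomitant Treatments/Therapy status"). A test follows, and 6.7(7) adds a multivariate logistic regression.

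**Drugs given because of an event.** SAP 6.6(2) has "Therapeutic prescription" as a category of other action taken for an adverse event. Protocol 7.3.2.1 makes the need for significant added concomitant drug or other therapy one of the criteria by which an abnormal test result becomes an adverse event.

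**The concern.** A factor that is said to affect an outcome should be fixed before the outcome occurs. This one need not be. A subject on no other drug who has a headache and is given an analgesic can move from No to Yes because of the adverse event. For abnormal test results that qualify as adverse events because they led to added therapy, the status is Yes almost by definition, so that part of the comparison is circular.

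Multivariable adjustment does not remove this, because the fault lies in how the exposure is defined and not in an omitted covariate.

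At stake is the reading of the re-examination report to the MFDS. An odds ratio above 1 with a small p-value, under a heading about factors that affect safety, could be taken as evidence that concomitant medication raises the risk of adverse events or interacts with the product.

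**Working it through.** The plan has no figure to reproduce here: "The calculation of sample size is not applicable for this study" (Protocol 7.5). The only stated error rate is two-sided 5%.

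**Inputs from the documents**
- Subjects: n = 86 (Protocol 5: "safety and efficacy information for at least 86 subjects will be collected").
- Test: Fisher's exact or Chi-square, two-sided 5% (SAP 5.1 and 6.6(4)).

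**Assumed inputs (the documents give none)**
- q, proportion of subjects with an adverse event: 10%, 20% or 30%.
- c, proportion Yes for reasons unrelated to any event: 30%, 50% or 70%.
- t, proportion of subjects with an adverse event who receive a drug for it that is counted in the status: 25%, 50% or 75%. If the case report form keeps such drugs out of the status, t = 0.

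**Null model.** Background use has no effect on adverse events. Then:
- P(Yes | event) = c + (1 − c)t
- P(Yes | no event) = c
- Expected odds ratio = odds[c + (1 − c)t] / odds[c]

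The odds ratio does not depend on q and exceeds 1 whenever t > 0.

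**Middle case: q = 20%, c = 50%, t = 50%**
- P(Yes | event) = 0.5 + 0.5 × 0.5 = 0.75, so the odds ratio = (0.75/0.25)/(0.5/0.5) = 3.00.
- Subjects with an event: 86 × 0.2 = 17.2, of whom 12.9 are Yes and 4.3 No. Subjects without: 68.8, of whom 34.4 are Yes and 34.4 No.
- Event incidence in Yes: 12.9/47.3 = 27.3%. In No: 4.3/38.7 = 11.1%.
- False-positive rate: 40% (Fisher) or 47% (uncorrected Chi-square).

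**Expected odds ratio with no true effect**

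| Background use c | t = 25% | t = 50% | t = 75% |
|---|---|---|---|
| 30% | 2.11 | 4.33 | 11.00 |
| 50% | 1.67 | 3.00 | 7.00 |
| 70% | 1.48 | 2.43 | 5.29 |

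**Fisher false-positive rate in %, n = 86, 10,000 simulated studies per scenario; each cell gives q = 10 / 20 / 30%**

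| Background use c | t = 25% | t = 50% | t = 75% |
|---|---|---|---|
| 30% | 15.4 / 24.0 / 29.6 | 46.6 / 71.4 / 82.9 | 82.1 / 97.8 / 99.7 |
| 50% | 6.7 / 12.0 / 14.9 | 21.0 / 39.8 / 52.3 | 49.7 / 82.0 / 92.7 |
| 70% | 2.0 / 5.7 / 8.3 | 4.8 / 17.1 / 26.0 | 11.1 / 42.3 / 61.3 |

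**With event-driven drugs not counted (t = 0).** The expected odds ratio is 1.00. Rejection is 2.6–3.9% with Fisher and 4.4–5.2% with Chi-square, in line with the nominal level.

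**Efficacy, by reasoning only.** For prophylaxis, SAP 6.7(4) counts a subject as not effective after an atypical bleed within 48 hours of a dose. A drug given for that bleed can turn the status to Yes, as in the safety case. For on-demand treatment the outcome is best response, and subjects in both outcome groups have a bleed or surgery. A drug given for the bleed does not by itself separate the groups. Bias there needs drugs added because the response was poor.

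**The case against.** **The status may not contain these drugs.** SAP 4.4 and 6.4 do not say that it does, treatment of an adverse event has its own field in SAP 6.6(2), and the case report form is not among the documents. This stands as a limit on wording: the plan does not exclude event-driven drugs, but it cannot be shown to include them. It does not dispose of the point, because Protocol 7.2.5.2 covers all concomitant therapies and nothing in the SAP removes them.

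**A false finding is not assured.** A reader might infer that the report will, or probably will, declare a false effect. The documents do not support that. Every driving rate is assumed. With 70% background use, 10% adverse events and 25% treated, rejection is 2.0%, although the expected odds ratio is still 1.48.

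**Efficacy is not equally affected.** A reader might carry the safety result over to SAP 6.7(6)–(7). The bleed mechanism fits prophylaxis and not on-demand best response, and no size was computed.

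**Distortion of the other odds ratios is not established.** A reader might infer that every factor in the safety model is adjusted for a post-event variable. SAP 6.6(5) does not clearly specify a joint model; only 6.7(7) calls its regression multivariate.

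**These are secondary analyses.** Protocol 7.7.2 makes the analysis mainly descriptive, with testing if the data are adequate, and Protocol 7.9 says that the SAP follows MFDS guidelines. That limits the importance. It does not remove the point, because the SAP prescribes the tests, p-values and odds ratios and words them as factors that affect safety.

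**Conclusion.** The concern holds for safety. As defined, concomitant status can be a consequence of the adverse event, and its association with adverse events is biased upward whenever event-driven drugs count towards it. With no true effect and 86 subjects, the expected odds ratio is about 1.5 to 11. The Fisher false-positive rate runs from about nominal to over 90%, and is 40% in the middle case. These sizes rest on the assumed rates for adverse events, background use and drug-treated events. The direction of the bias does not depend on them.

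A significant false finding is possible but not certain. For efficacy the point is weaker: plausible for prophylaxis, conditional on drugs added after a poor response for on-demand treatment, and unquantified in both. The primary objective, detection of factor VIII inhibitors, is unaffected. The change should be made because planned inferential outputs could mislead and the data needed are already recorded.

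**What to change.** **SAP 4.4 and 6.6(4)–(5).** Derive the analysed status from the period and purpose recorded under Protocol 7.2.5.2. Count only drugs and therapies ongoing at the first Solofuse infusion and not given for an adverse event. Tabulate event-driven treatments separately, under other action taken. The full Yes/No listing in SAP 6.4 can stay as description.

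**SAP 6.7(6)–(7), prophylaxis.** Use the same status, ongoing at first infusion.

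**SAP 6.7(6)–(7), on-demand.** Do not exclude adjunct treatment given with the infusion for the bleed or surgery. The bleed normally precedes the infusion, so a rule that dropped everything started after the bleed would remove the exposure most relevant to response. Exclude only drugs added after a response was rated, and present the comparison descriptively.

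**Cost.** SAP wording and a derived variable, with no new data collection. Fewer subjects count as Yes, so intervals for this factor widen. Drugs started after the first infusion but before an event are not counted as exposure, which loses some genuine exposure. The recorded purpose needs some review rather than a purely mechanical rule.
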